7.5 Ethics	25
8.0 RegistrationProcedures	25
8.1 GeneralGuidelines	25

8.2 RegistrationProcess	25
9.0 ProtocolConductandGuidelines	26
9.1 Protocolamendments,orchangesinstudyconduct	26
9.2 Publicationofresults	26
9.3 EthicsandGoodClinicalPractice	26
9.4 InstitutionalReviewBoard/IndependentEthicsCommittee	26
9.5 Informedconsent	26
9.6 DeclarationofHelsinki	27
10.0 References	28
11.0 Appendix	30
11.1 KarnofskyPerformanceScale	31
11.2 WeeklyToxicityScoringSheet	32
11.3 LLLTTreatmentRecordForm	33
11.4 Table2.ConsensusContouringGuidelinesforOrgansatRisk	38
11.5 Table3.OARdoseparameterstoberecorded	40
11.6 FACT-G(Version4)	41
11.7 FACT-H&N(Version4)	43
11.8 OralMucositisDailyQuestionnaire	44
11.9DataandSafetyMonitoringReport	45
11.10 Study Calendar	47

Study Schema

A phase II, single-arm trial to examine the efficacy of prophylactic low-level laser therapy (LLLT) to reduce the incidence of oral mucositis and adverse events in patients receiving combined modality therapy consisting of chemotherapy and radiation therapy for head and neck cancer.

Patients meeting the eligibility criteria will be enrolled to receive prophylactic LLLT in addition to standard of care measures for oral mucositis or other toxicity of therapy. The radiation and chemotherapy dose, schedule, modality, technique, and any required adjustments will not be influenced by this protocol and will follow standard existing institutional practices.

Patients will receive LLLT three times per week concurrently with chemoradiotherapy. LLLT may be delivered either immediately prior to or after the patient's daily fraction of radiotherapy. Patients will be treated extra-orally with a THOR® LED cluster for one minute along the buccal mucosa on each side and intraorally for one minute to the tongue and soft palate. During each LLLT treatment session a thorough oral exam will be performed to identify any areas of mucositis. If the patient should develop intraoral lesions they will be targeted directly with the intraoral probe for one minute to each site of mucositis. The laser settings to be used are as follows: frequency 2.5 Hz; wavelength 660 nm; and power 75 mW, for an energy of 4.5 J.

Patients will be evaluated prior to therapy, weekly during therapy, two weeks after the completion of therapy, and three months after the completion of therapy. During each assessment, the following toxicities will be assessed: pain, mucositis, dysphagia, xerostomia, dysgeusia, dermatitis, trismus, and quality of life.

Previous studies indicate that approximately 40% of patients will experience severe mucositis with radiation and concurrent chemotherapy. The hypothesis in this trial is that the addition of LLLT to this treatment regimen will decrease the rate of severe acute OM to 20%. We plan to enroll 25 patients at our institution in 12 months after the trial opens. The same protocol will be opened separately at the University of Pittsburgh Medical Center (UPMC), where an additional 25 patients will be enrolled. A Data Use Agreement will allow combination of the data for a total of 50 patients to be analyzed.

1.0 Objectives:

1.1 PrimaryObjective

Our primary objective is to determine the ability of low-level laser therapy (LLLT) to reduce the rates of severe oral mucositis in patients receiving radiation with concurrent chemotherapy for head and neck cancer (HNC).

1.2 SecondaryObjectives

1. To establish the time to onset of severe oral mucositis following the initiation of radiotherapy with LLLT.
2. To determine the incidence of pain, dysphagia, xerostomia, dysgeusia, trismus, radiodermatitis, and OM-related QOL (via FACT-H&N score) with LLLT.
3. To evaluate the mean cumulative radiation dose at time of onset of severe oral mucositis with LLLT.
4. Determine the duration of oral mucositis.
5. Record the amount of narcotic analgesia use during treatment.
6. Evaluate the number of breaks in chemoradiotherapy with LLLT use.
7. Determine the proportion of patients who require feeding tube placement during treatment.

2.0 Introduction

2.1 DiseaseOverview

Combined modality therapy with chemotherapy and radiation is a commonly employed treatment approach for patients with various types of HNC [1]. Despite the overall safety and efficacy of this treatment modality, side effects exist, including acute chemoradiation-induced pain, dermatitis, xerostomia, dysgeusia, dysphagia, odynophagia, and oral mucositis. In fact, a majority of patients treated with this modality will experience some degree of oral mucositis (OM) [2]. OM can affect many oral functions including mastication and swallowing which may lead to dehydration, renal failure and necessitate the placement and use of a feeding tube and negatively impact and patient's quality of life (QOL). Severe OM can also predispose a patient to increased risk of infections requiring hospitalization and increased cost of treatment [3]. The severity of these reactions can be so severe that patients who experience treatment-related mucositis are less likely to complete the planned course of therapy without unplanned interruptions in therapy. Previous studies provide evidence that unplanned breaks in radiotherapy for HNC result in worse tumor control [4]. Furthermore, adverse events can increase the cost of healthcare by resulting in preventable hospital admissions for intravenous hydration and nutritional support and procedures including feeding tube placement. In fact, OM has

been shown to be associated with an incremental cost of \$1,700 - \$6,000 per patient, depending on the grade [5].

Despite multiple clinical trials, no single treatment has been proven to be effective in substantially reducing incidence or severity of chemoradiation induced oral mucositis. The current standard practice for the management of OM is symptom management and supportive care with narcotic pain medications and anesthetic mouth rinses and nutritional support with supplementation either by mouth or feeding tube.

2.2 ProductBackground

Photomedicine utilizing low level laser (or “light” as light emitting diode sources are increasingly being used in place of lasers) therapy (LLLT) has been investigated as a novel therapeutic approach since the 1960s. LLLT is a safe, low-intensity form of light therapy. LLLT employs visible (generally red) or near-infrared light generated from a laser or light emitting diode (LED) [6]. Therapy with LLLT has been shown to relieve pain, reduce inflammation, and improve tissue repair. LLLT does not function through ablative or thermal mechanisms, but rather a photochemical effect comparable to photosynthesis in plants whereby the light is absorbed and exerts a chemical change [6].

LLLT was first completely limited to treatment with laser sources, such as the helium neon (HeNe) or indium phosphide, gallium and aluminum diode (InGaAIP) lasers. The non-coherent light produced by light emitting diode (LED) devices has the same biological properties and clinical effectiveness as coherent light produced by lasers, with the advantages of LED technology being that it is significantly less expensive and can be arranged in arrays permitting greater surface area exposure and subsequent shorter overall treatment times. Furthermore, LED-based LLLT applied extraorally has good penetration through skin and soft tissue to the oral mucosa [7]

2.3 ProductMechanismofAction

The mechanism of action no LLLT is rooted in photochemistry. Light photons must be absorbed by molecular photoacceptors or chromophores for photochemistry to occur [8]. The cellular mechanism of LLLT has been attributed to the absorption of monochromatic visible and near infrared (NIR) radiation by the cellular respiratory chain [9].

Phototherapy is characterized by its ability to induce photobiological processes in cells. Mitochondria play a crucial role in cellular metabolism and the generation of energy in the form of adenosine triphosphate (ATP) through oxidative phosphorylation.

Mitochondria have been studied as the main target of phototherapy. Cytochrome c oxidase is the proposed photoacceptor for the red-NIR light range in mammalian cells, as absorption spectra for light were found to be similar to the absorption spectra of cytochrome c oxidase [10]. LLLT to isolated mitochondria increased ATP synthesis, RNA and protein synthesis, and enhanced synthesis of NADH and ATP [6]. In stressed tissues, mitochondria make nitric oxide that competes with oxygen in the oxidative phosphorylation chain. This in turn decreases ATP synthesis and can increase production

of reactive oxygen species (ROS), which are small molecules that are highly reactive with proteins, nucleic acids, and lipids. ROS are potentially harmful to intracellular elements and their formation triggers cellular sensors that can engage signaling pathways involved in gene transcription (such as nuclear factor κ B (NF- κ B). While the exact mechanism of action is unknown, LLLT has been shown to interact with cytochrome c oxidase in mitochondria to release nitric oxide, facilitating oxidative phosphorylation. This increases ATP production and stimulates downstream signals to produce antioxidants and growth factors for cellular repair and proliferation. As a result, LLLT has been shown to decrease pain and inflammation and promote wound healing and tissue repair.

2.4 ProductEfficacy

LLLT is a non-invasive technique which has been examined for the prevention and treatment of radiotherapy-induced OM. Multiple randomized trials have shown a reduction in the rates of OM and pain with the use of LLLT [11-20]. A list of trials examining the impact of LLLT for OM prevention in patients with HNC is given in table 1.

Furthermore, a systematic review and meta-analysis of eleven randomized placebo-controlled trials of LLLT use during chemotherapy or radiation therapy in HNC patients was performed [21]. This found a relative risk for developing OM was significantly ($p=0.02$) reduced after LLLT compared with placebo. The number of days with OM grade 2 or worse was also significantly reduced after LLLT to 4.38 days less than placebo. Likewise, OM severity was reduced after LLLT compared with placebo. All studies in this meta-analysis recorded possible adverse effects of LLLT therapy, but there were no differences from treatment with placebo. Evidence from these small, randomized controlled trials shows a significant reduction in incidence and severity of OM for HNC patients.

Additionally, the Multinational Association of Supportive Care in Cancer and International Society of Oral Oncology (MASCC/ISOO) Clinical Practice Guidelines for Mucositis recommends in favor of LLLT for the prevention of OM in patients receiving high-dose chemotherapy for hematopoietic stem cell transplants with or without total body irradiation and a suggestion for LLLT in the prevention of OM in patients receiving RT for HNC [22]. No guideline was issued for patients receiving concurrent chemotherapy and radiation therapy for HNC due to lack of high-level evidence. The European Society for Medical Oncology (ESMO) clinical practice guidelines for the management of oral and gastrointestinal mucositis also advises the use of LLLT to reduce the incidence of oral mucositis and its associated pain, in patients receiving high-dose chemotherapy or chemoradiotherapy before hematopoietic stem cell transplant [23].

Table 1. LLLT trials for oral mucositis prevention

Reference	Population	Methods	Treatment	Results	Comments
Antunes et al Radiother Oncol 2013[11]	HNC (n=94) Brazil, 2007-2010	Phase III, randomized placebo controlled trial	Concurrent Chemoradiotherapy (1) Placebo~ (2) LLLT daily prior to each RT fraction Chemo: cisplatin 100 mg/m ² q3weeks RT: 70.2 Gy LLLT: InGaAIP, 660 nm, 100mW, 1-4J/cm ²	Grade 3-4 mucositis (WHO): 40.5% vs. 6.4% Relative risk: 0.16 (0.05-0.5)	Improved QOL for pain, swallowing and difficulty with eating
Arora et al Oral Surg Oral Med Oral Pathol Oral Radiol Endod 2008[13]	Oral cancer (n=50) India, 2005-2006	Phase III, randomized controlled trial	Radiation (1) Topical anesthetic, saline washes~ (2) LLLT daily prior to RT RT: 66 Gy LLLT: He-Ne, 632.8 nm, 10mW, 1.8J/cm ²	Grade 3-4 mucositis (EORTC/RTOG) 53.9% vs. 18.2% at 3 weeks (p=0.019)	Functional impairment Scale maximum score: Oral alimentation not possible: 31% vs. 0%
Bensadoun et al Support Care Center 1999[14]	HNC (n=30) France, 1994-1998	Phase III, randomized placebo controlled trial	Radiation (1) Placebo~ (2) LLLT prior to each RT fraction RT: 65 Gy LLLT: He-Ne, 632.8 nm, 60mW, 2J/cm ²	Grade 3 mucositis (WHO): 35.2% vs. 7.6% (p<0.01) Severe pain: 23.8% vs. 1.9% (p<0.05)	
Gautam et al Radiother Oncol 2012[16]	HNC (n=221) India, 2009-2011	Phase III, randomized placebo controlled trial	Concurrent Chemoradiotherapy (1) Sham treatment~ (2) LLLT 5x/week, prior to or following RT Chemo: cisplatin 100 mg/m ² q3weeks RT: 66 Gy LLLT: He-Ne, 632.8 nm, 24mW, 3J/point	Grade ≥3 mucositis (EORTC/RTOG): 70% vs. 23.4% (p < 0.0001)	Pain scores plateaued after week 4 in LLLT arm and continued to increase in placebo arm Lower dysphagia in LLLT arm
Zanin et al Photomed Laser Surg 2010[18]	HNC (n=72) Brazil	Phase III, randomized controlled trial	Concurrent Chemoradiotherapy (1) No treatment~ (2) LLLT 2x/week, prior to or following RT Chemo: cisplatin~70 mg/m ² weekly RT: 1.8 Gy daily fractions LLLT: He-Ne, 660 nm, 30mW, 2J/cm ²	Mucositis (NCI) significantly lower in LLLT group from week 1 to week 4 (p=0.001), but remained stable until week 7 (p=0.68)	LLLT delayed onset of oral mucositis
Lima et al, Braz Dent J 2010[17]	HNC (n=25) Brazil, 2005	Prospective, non- randomized study	RT ± chemotherapy (1) Sucrose and aluminum hydroxide suspension~ (2) LLLT daily prior to each RT fraction Chemo: cisplatin 100mg/m ² q3weeks RT: 40-70 Gy LLLT: 830 nm, 60 mW, 12.4J/cm ²	Grade 3 mucositis (OTS Scale) OM 50% vs. 33% (p=0.06)	Significant decrease in pain with LLLT (p=0.036)

HNC; head and neck cancer. LLLT; low-level laser therapy. RT; Radiation. Gy; Gray. InGaAIP; indium phosphide, gallium and aluminum diode. nm; nanometer. mW; milliwatts. J; Joules. WHO; World Health Organization. QOL; Quality of Life. He-Ne; Helium-Neon. EORTC; European Organisation for Research and Treatment of Cancer. RTOG; Radiation Therapy Oncology Group. NCI; National Cancer Institute.

2.5 ProductSafety

Lasers used for LLLT are categorized as Class 3b. Class 3b lasers emit 5mW to 500mW lasers, with some emitting infrared light below 5mW. A class 3b laser may be hazardous under direct and specular viewing conditions, but is not a fire hazard. The patient and LLLT operator require use of protective eyewear. The LLLT system is equipped with a key switch and a safety interlock. The THOR® Laser system (THOR Photomedicine Ltd, Chesham, UK) that will be used to deliver LLLT in this protocol is an FDA-approved medical device (510(K) number K030226).

There has been no reported toxicity in any of the studies of LLLT for the prevention and/ or management of oral mucositis. In the limited number of studies evaluating extraoral LLLT, there has similarly been no reported cutaneous or oral toxicity.

2.6 RationalefortheStudy

Previous phase III trials conducted in other countries, primarily Brazil [11], France [14], and India [16], have shown a significant improvement in OM with LLLT. However, no U.S. trials have been reported. The rationale for this phase II trial is to validate the results from international trials in a U.S. cohort of patients. Therefore, our goal is to evaluate the efficacy of LLLT in reducing treatment related toxicities including OM, pain, xerostomia, dysgeusia, and dysphagia and improving OM-related QOL in patients undergoing radiation with chemotherapy for HNC. To accomplish our goal, we propose a prospective, single-arm, phase II trial with the aim of improving health-care quality and reducing the incidence of treatment-related toxicity as compared to historical controls. The same protocol will be opened separately at the University of Pittsburgh Medical Center (UPMC). A Data Use Agreement will allow for a combination of the data from both centers to be analyzed.

3.0 SelectionandWithdrawalofSubjects

3.1 StudyDesign

This is a phase II prospective, single-arm, open label trial testing the efficacy of LLLT in prevention of oral mucositis for HNC patients treated with chemoradiotherapy. Primary endpoints are the incidence of severe (assessed separately as CTCAE v. 4.0 grade 3-5 or WHO grade 3-4) OM in patients receiving a cumulative radiation dose of at least 5000 cGy. Secondary endpoints include the time onset to severe OM, mean cumulative radiation dose at the time of OM, duration of OM, the incidence of pain, dysphagia, xerostomia, dysgeusia, trismus, radiodermatitis, and QOL.

All toxicities will be graded by NCI CTCAE v. 4.0. In addition, oral mucositis will also be graded by WHO mucositis grading scale. Dysphagia will also be graded by a dietary assessment. Trismus will be assessed by measurements of the interincisal distance. QOL will be measured by the FACT-H&N assessment.

Previous studies (detailed in Section 2.2, Table 1) indicate that approximately 40% of patients will experience severe OM with radiation and concurrent chemotherapy. The hypothesis in this trial is that the addition of LLLT to this treatment regimen will decrease the rate of severe acute OM to 20%. We plan to enroll 25 patients at our institution in 12 months after the trial opens. The same protocol will be opened separately at the University of Pittsburgh Medical Center (UPMC), where an additional 25 patients will be enrolled. A Data Use Agreement will allow combination of the data for a total of 50 patients to be analyzed.

3.2 PatientSelection

InclusionCriteria:

1. Willing and able to understand and sign informed consent form approved by the IRB.
2. Males or females greater than or equal to 18 years old.
3. Biopsy-proven HNC including cancers of the nasopharynx, oropharynx, larynx, hypopharynx, or HNC of unknown primary origin amenable to therapy with radiation and concurrent chemotherapy.
4. Patients who are planned to receive definitive or adjuvant radiotherapy with concurrent platinum-based chemotherapy.
5. Patients whose clinical treatment plans include a continuous course of external beam radiotherapy by intensity-modulated radiation therapy (IMRT) and/or image-guided radiation therapy (IGRT), given as a cumulative dose of 5000 – 7000 cGy in single daily fractions of 180 - 200 cGy, combined with a concurrent course of weekly or tri-weekly cisplatin or carboplatin chemotherapy.
6. Karnofsky performance status score >60.
7. Female patients of child-bearing potential must have a negative pregnancy test prior to enrollment.

ExclusionCriteria:

1. Patient has evidence of current mucositis, mucosal ulceration, or unhealed surgical wounds from surgical resection or biopsy.
2. Prior radiation to the head and neck.
3. Patients with gross tumor involvement of the oral cavity or oral mucosa.
4. Patient planned to receive altered fractionation radiotherapy or multiple fractions per day
5. Patient is using a pre-existing feeding tube for nutritional support at the time of study entry.
6. Women who are pregnant or breast-feeding.
7. Patient plans to receive concurrent chemotherapy, other than the regimens specified in the inclusion criteria.
8. Patients who have chronic immunosuppression or are on current immunosuppressive therapies.
9. Patients who have a contraindication to radiation therapy.
10. Patients enrolled on another investigational trial for oral mucositis prevention.
11. Life expectancy of less than 3 months.
12. Unable or unwilling to adhere to study-specified procedures.

3.3 Withdrawal of Subjects

Any subject, having previously provided informed consent to participate in the protocol, is free to withdraw from the study at any time for any reason without prejudice to their future medical care by the physician or at the study site. The Investigator or Sponsor may also withdraw the subject at any time in the interest of subject safety. The primary reason for withdrawal must be recorded.

Subject participation may be terminated prior to completion of the clinical study for any of the following reasons:

1. Unacceptable toxicity
2. Death
3. Lack of efficacy
4. Withdrawal by subject
5. Lost to follow-up
6. Non-compliance with study treatment (Subjects who miss >20% of planned LLLT treatments will be considered non-compliant with the protocol)
7. Study physician decision in the best interest of subject safety
8. Pregnancy
9. Major protocol deviation that can affect the safety or efficacy of study population
10. Study terminated
11. Other

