4.0 Treatment Methods

4.1 Radiation Treatment

Prior to treatment, all patients will provide informed written consent for radiation therapy as per existing institutional policy. All patients will undergo a computed tomography (CT) simulation for treatment planning. Radiation therapy will be delivered with an intensity modulated radiation therapy (IMRT) technique and/or image-guided radiation therapy (IGRT). The prescribed course of radiotherapy will not be altered based on this study. Radiotherapy will be delivered 5 days per week, Monday – Friday with one radiation treatment given per day. The planned cumulative dose of radiation will be determined by the treating physician and will range from 5000 – 7000 cGy in 180 - 200 cGy daily fractions over the course of 5-7 weeks. This treatment is not part of the research protocol.

4.1.1 Definition of Target Volumes:

Target volumes will be outlined per institutional practice and not modified based on this protocol. Target volumes are defined as the following:

Gross Tumor Volume (GTV) represents the region judged to contain gross primary tumor or involved node(s) based on clinical and endoscopic examinations, CT scan, and, when applicable, other imaging techniques.

Clinical Target Volume (CTV) is defined as the GTV plus areas considered at risk for containing microscopic disease delineated by the treating physician. The CTV margins can be narrower when GTV is in the proximity of the spinal cord or critical normal tissues.

Planning Target Volume (PTV) represents an additional margin around the CTV to compensate for the variability of treatment set up and internal organ motion.

4.1.2 Definition of Organs at Risk:

CT-based planning will be used to identify the target volumes and organs at risk (OARs). OARs will be contoured according to the DAHANCA, EORTC, GORTEC, HKNPCSG, NCIC CTG, NCRI, NRG Oncology, and TROG consensus guidelines [24] which are included in table 2 which is provided in appendix 11.4. The dose parameters given to OARs will be recorded (table 3). Dose limits to OARs will be determined by institutional practice and specific dose-constraints will not be required on this protocol. The following radiation doses will be recorded.

Table 3. Dose parameters to OARs to be recorded

Brainstem	Maximum Dose _____
Spinal Cord	Maximum Dose _____
Right Parotid	Mean Dose _____
	V30 _{Gy} _____
Left Parotid	Mean Dose _____
	V30 _{Gy} _____
Parotids (bilateral)	D20 _{cc} _____

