4.3 Low-LevelLaserTherapy

Treatment will be administered on an outpatient basis. While there are no expected toxicities, potential adverse events will be monitored per Section 7 (Adverse Events and Safety Monitoring). No investigational agents or therapies for the prevention of oral mucositis other than those described in this protocol may be administered.

LLLT will be delivered with the THOR® Laser system (THOR Photomedicine Ltd, Chesham, UK). LLLT will begin on the first or second day of radiotherapy and be delivered three times per week (e.g. Monday, Wednesday, and Friday) until the completion of radiotherapy. A trained radiation oncology nurse or physician will deliver treatment. LLLT may be delivered either immediately prior to or after the patient's daily fraction of radiotherapy. If it is determined that a break in radiotherapy is required for clinical reasons, LLLT will also be held. Patients will be treated extra-orally with a THOR® LED cluster for one minute along the cheek to treat the buccal mucosa on each side and intraorally for one minute to the tongue and soft palate. During each LLLT treatment session a thorough oral exam will be performed to identify any areas of mucositis. If the patient should develop intraoral lesions they will be targeted directly with the intraoral probe for one minute to each site of mucositis.

The laser settings to be used are as follows: frequency 2.5 Hz; wavelength 660 nm; and power 75 mW. The dose per anatomic site treated will be 4.5 J/cm². No dose modifications for the LLLT will be made.

The extra-oral probe will be cleaned before and after each use. Prior to each use, the intraoral probe will be covered with a protective dental sleeve. Patients and laser operator will wear THOR® laser safety glasses for the duration of laser therapy.

Treatment dates and sites will be recorded for each patient on the LLLT Treatment Record Form given in the appendix (appendix 11.3). Compliance with therapy will be documented. Subjects who miss >20% of planned LLLT treatments will be considered non-compliant with the protocol. For each treatment session, the dose will be set (timer on control unit) and the patient will be positioned comfortably a chair. The LLLT device will be for a minimum of 3 exposures:

1. Right cheek
2. Left cheek
3. Tongue/Soft palate

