4.4 Other treatments

Subjects that develop symptomatic mucositis will be managed as necessary according to standard standard of care hospital protocol for oral mucositis in addition to LLLT. This may include topical creams, pain medications, anesthetic mouth rinses, mouth coatings, and nutritional support with supplementation either by mouth or feeding tube, without the use of specific investigational, restricted agents. No standard treatment will be denied to a patient on this protocol.

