5.0 Follow-up and Assessments

5.1 Followup Schedule

A general history & physical by a radiation oncologist and/or medical oncologist must be done within 8 weeks prior to registration. Patients will be evaluated for protocol eligibility at the time of initial consultation. At the time of initial evaluation, baseline assessments will be performed. During the course of treatment, each patient will be seen by the supervising physician in clinic for an on-treatment evaluation at least once per week (or at an interval of once per five radiation treatments). Follow-up appointments will be scheduled for two weeks and three months after the completion of therapy.

Table 4. Study Calendar Overview

Screening	Baseline	Treatment Period		Follow-up Period
		Assessments	LLLT Dosing	
Day -1 to Day -28	Study Day 0	Weekly Last day of treatment	3x/week concomitant with chemoradiation	Two weeks Three months

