6.0 Statistical Considerations

6.1 Primary Endpoints:

- The incidence of severe (WHO grade 3-4) oral mucositis in patients treated to a cumulative radiation dose of at least 5000 cGy.
- The incidence of severe (CTCAE v. 4.0 grade 3-5) oral mucositis in patients treated to a cumulative radiation dose of at least 5000 cGy.

6.2 Secondary Endpoints:

- Time to onset of severe (CTCAE v. 4.0 grade 3-4) oral mucositis following the initiation of radiotherapy.
- Mean cumulative radiation dose at time of onset of severe (CTCAE v. 4.0 grade 3-4) oral mucositis.
- Duration of oral mucositis.
- The incidence of pain.
- The incidence of dysphagia (CTCAE v. 4.0 and via diet assessment).
- The incidence of xerostomia (CTCAE v. 4.0).
- The incidence of dysgeusia (CTCAE v. 4.0).
- The incidence of trismus (Measurement of interincisal distance).
- The incidence of radiodermatitis (CTCAE v. 4.0).
- Evaluation of OM-related QOL (via FACT-H&N score).
- Incidence of any grade oral mucositis in patients treated to a cumulative radiation dose of at least 5000 cGy.

6.3 Exploratory Endpoints:

- Proportion of patients with severe (CTCAE v. 4.0 grade 3-4) oral mucositis by 5000 and 7000 cGy.
- Proportion of patients with severe (CTCAE v. 4.0 grade 3-4) oral mucositis by schedule of chemotherapy given (weekly versus Q 3 weeks).
- Time to reach planned dose of radiation therapy.
- Amount of narcotic analgesia use during treatment.
- Assessments of breaks in treatment defined as one of the following:
 - Missing at least 1 chemotherapy treatment;
 - Dose reduction in planned cisplatin administration; OR
 - 3 consecutive days of no RT secondary to mucositis. ~
- Proportion of patients who require feeding tube placement during treatment (excluding patients who received a prophylactic feeding tube prior to the initiation of therapy).
- Percent change in body weight during the course of treatment.

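### Section 3.3 lets a patient leave the study, not only stop LLLT, for undefined lack of efficacy or missed sessions, and no text expressly continues scheduled mucositis grading afterwards

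*Combined protocol and SAP*

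**What the plan says.** - **Exit.** Section 3.3 opens its list with "Subject participation may be terminated prior to completion of the clinical study for any of the following reasons". Reason 3 reads "3. Lack of efficacy" and has no criterion here or elsewhere. Reason 6 begins "Non-compliance with study treatment (Subjects who miss >20% of planned LLLT treatments will be considered non-compliant with the protocol". What ends is participation; stopping LLLT alone is not a separate category. The list is permissive, and the primary reason for withdrawal must be recorded.
- **Radiotherapy.** Section 4.1: "The prescribed course of radiotherapy will not be altered based on this study". A patient who leaves stays at risk of severe OM.
- **Mucositis on study.** Section 4.3: "If the patient should develop intraoral lesions they will be targeted directly with the intraoral probe for one minute to each site of mucositis". Section 4.4 manages symptomatic mucositis by the "standard of care hospital protocol for oral mucositis in addition to LLLT".
- **Assessment.** Section 5.1: "each patient will be seen by the supervising physician in clinic for an on-treatment evaluation at least once per week". The sheet in 11.2 carries both the WHO and the CTCAE mucositis scales. Section 7.1 continues adverse-event monitoring for at least 3 months after the last LLLT, 7.2 follows a detected event until it resolves, and the 11.10 calendar lists oral mucositis in its CTCAE adverse-event row. WHO grading is a separate calendar row.
- **Who counts.** Section 6.1 has two primary endpoints, one by CTCAE grade 3-5 and the other "The incidence of severe (WHO grade 3-4) oral mucositis in patients treated to a cumulative radiation dose of at least 5000 cGy". Neither has an LLLT-compliance condition. Section 6.4 enrols 50 to secure 45 compliant patients. Section 6.5 rejects the null at 12 or fewer events in 45 evaluable patients and does not define evaluable.

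**The concern.** Lack of efficacy, in a trial meant to prevent severe mucositis, is close to the primary outcome itself. With no blinding and no control arm, whoever ends participation knows how the patient's mouth looks. If a worsening patient leaves before grade 3 is recorded and is not graded again, a likely event is lost and the observed rate falls, in favour of LLLT.

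Missed sessions are a different route. At three sessions a week for 5, 6 or 7 weeks, the planned totals are 15, 18 and 21, so more than 20% missed means 4, 4 or 5 sessions. Whether such patients are at higher or lower risk depends on why they missed them.

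A separate difficulty follows. A patient who misses more than 20% of LLLT but receives at least 5000 cGy belongs to the 6.1 population, yet is not one of the 45 compliant patients on whom 6.4 sizes the test. Even a fully recorded event may or may not count.

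**Working it through.** **1. The plan's own figure.** Inputs from 6.4 and 6.5: null rate 0.40, target rate 0.20, n = 45, one-sided exact binomial test at 0.05, reject at 12 or fewer events.

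- Type I error: P(X ≤ 12 | 45, 0.40) = 0.0446; a cutoff of 13 would give 0.0836.
- Power: P(X ≤ 12 | 45, 0.20) = 0.9005.
- Enrolment: 45 / 0.90 = 50.

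The design reproduces.

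**2. Effect of ungraded exits.** Assume 50 enrolled and a true overall rate of 0.40, so 20 severe cases are expected. Let L patients leave ungraded, each with severe-OM risk r. The remaining 50 − L have rate (20 − L·r)/(50 − L). Apply the written cutoff of 12 to them. L and r are assumptions; the documents give neither.

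| L | Tested | r | Rate in those tested | P(X ≤ 12) |
|---|---|---|---|---|
| 1 | 49 | 1.0 | 19/49 = 0.3878 | 2.6% |
| 2 | 48 | 1.0 | 18/48 = 0.3750 | 4.8% |
| 3 | 47 | 1.0 | 17/47 = 0.3617 | 8.4% |
| 5 | 45 | 1.0 | 15/45 = 0.3333 | 21.7% |
| 5 | 45 | 0.8 | 16/45 = 0.3556 | 13.7% |
| 5 | 45 | 0.6 | 17/45 = 0.3778 | 8.1% |
| 5 | 45 | 0.4 | 18/45 = 0.4000 | 4.5% |
| 5 | 45 | 0.2 | 19/45 = 0.4222 | 2.3% |

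At the written cutoff, even leavers certain to develop severe OM push the error past 5% only from the third exit. With five exits it stays below 5% if leavers are at average or lower risk.

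If the cutoff were reset to the exact value for 48 tested (13), two exits at r = 1.0 would give 8.8%, against 4.4% at r = 0.4. The plan contains no such reset.

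**3. Effect of the choice of population.** Twelve events in 45 compliant patients rejects (p = 0.0446). If the five patients left out include two severe cases, the count is 14/50 and the null stands (p = 0.0540).

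**4. Cutoffs for other numbers analysed.** Section 6.5 gives a rule only for 45. The largest cutoff with exact alpha at or below 0.05:

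| Number analysed | Cutoff | Exact alpha |
|---|---|---|
| 42, 43, 44 | 11 | 0.0449, 0.0354, 0.0277 |
| 45, 46, 47 | 12 | 0.0446, 0.0354, 0.0279 |
| 48, 49, 50 | 13 | 0.0442, 0.0353, 0.0280 |

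**5. Power if LLLT stoppers are counted.** With n = 50 and cutoff 13, take 45 patients at 0.20 and five stoppers at an assumed rate s. The number of events is the sum of two independent binomials, and power is P(sum ≤ 13): 88.9% for s = 0.20, 80.8% for s = 0.40 and 70.5% for s = 0.60.

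**The case against.** A reader might infer that the plan removes treatment failures, or that grading stops when participation ends. The documents support neither. Termination is permitted, not required. A grade 3 already recorded is not erased by a later exit, and severe OM is the most natural meaning of lack of efficacy here. Bias therefore needs an exit for inefficacy before grade 3, whereas 4.3 and 4.4 treat mucositis with the probe and with standard care on top of LLLT. Milder mucositis is not a stated reason to stop. All of this stands, and it narrows the mechanism.

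Sections 5.1, 7.1, 7.2 and the 11.10 calendar also make continued CTCAE capture a fair inference, and CTCAE grade is one of the two primary endpoints. That stands too. What they do not do is mention patients terminated under 3.3, keep the weekly grading schedule for them, or cover the WHO grade, which is the other primary endpoint.

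A reader might take 21.7% as the trial's error rate. It is not: it needs five ungraded exits, all certain to develop severe OM. Five is the LLLT non-compliance margin in 6.4, not a forecast of ungraded exits, and for non-compliance the direction is unknown.

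Nor do 6.1, 6.4 and 6.5 set three rival rules. Sections 6.4 and 6.5 share the figure 45, and the mention in 6.4 of analysing 50 stands in a sentence about pooling two sites' data. The real difference is dose in 6.1 against compliance in 6.4, with evaluable left undefined.

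**Conclusion.** The point holds in limited form. Section 3.3 states a rule, not merely a missing detail, under which primary-endpoint follow-up can end for a reason close to the outcome itself, in an unblinded trial. The surrounding text makes loss of CTCAE grades less likely but does not exclude it, and protects the WHO grade least. Bias in favour of LLLT follows only for exits for inefficacy before grade 3 is recorded. At the written cutoff and r = 1.0, the false-success rate runs from 2.6% with one such exit to 21.7% with five; it depends wholly on the assumed number and risk of leavers.

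The difference between 6.1 and 6.4 is a related but separate gap. Splitting 3.3 and continuing grading is clearly worth doing. Moving the primary test from compliant patients to all who reach 5000 cGy is partly a trade-off, because it can cost power. The change should be made, though this is not a fatal flaw.

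**What to change.** **Section 3.3.** Split it into (a) discontinuation of LLLT and (b) withdrawal from the study. Limit (b) to consent withdrawn, loss to follow-up, death or study termination. Delete lack of efficacy as a reason for leaving. Treat toxicity, pregnancy, non-compliance and investigator or sponsor safety decisions, including those allowed by the opening paragraph of 3.3, as stopping LLLT. Patients in (a) continue WHO and CTCAE grading on the existing 11.2 sheet, radiation dose recording, and the two-week and three-month visits.

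**Section 6.5, with 6.4 aligned.** State that severe OM recorded after LLLT stops counts for patients in the 6.1 population. Report the compliant-only result alongside. List patients below 5000 cGy with their highest grade, since a severe case who stops radiotherapy early falls outside 6.1. Use the largest cutoff with exact alpha at or below 0.05 for the number analysed, as in step 4.

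**Cost.** A short amendment and a few more existing forms and visits. A reader might infer from the 88.9% at n = 50 that power drops by only about one point; that assumes patients who stopped LLLT still have a 20% rate. The sponsor should accept and state the lower figures in step 5 as well.
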